4. ENDPOINTS

4.1. Primary endpoints

- Immunogenicity with respect to components of *Infanrix hexa*.
 - Anti-diphtheria, anti-tetanus, anti-HBs, anti-poliovirus type 1, anti-poliovirus type 2, anti-poliovirus type 3 and anti-polyribosyl-ribitol phosphate (anti-PRP) seroprotection status, one month after the last dose of primary vaccination.

A seroprotected subject is a subject whose antibody concentration/titre is greater than or equal to the level defining clinical protection. The following seroprotection thresholds are applicable:

 - Anti-diphtheria antibody concentrations ≥ 0.1 IU/mL.
 - Anti-tetanus antibody concentrations ≥ 0.1 IU/mL.
 - Anti-HBs antibody concentrations ≥ 10 mIU/mL.
 - Anti-poliovirus types 1, 2 and 3 antibody titres ≥ 8 .
 - Anti-PRP antibody concentrations ≥ 0.15 $\mu\text{g/mL}$.
 - Vaccine response to PT, FHA and PRN antigens, one month after the last dose of primary vaccination.

Vaccine response to the PT, FHA and PRN antigens, is defined as:

- appearance of antibodies in subjects who were initially seronegative (i.e., with concentrations $<$ cut-off value).
- at least maintenance of pre-vaccination antibody concentrations in subjects who were initially seropositive (i.e., with concentrations \geq cut-off value).

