9. CHANGES FROM PLANNED ANALYSES

- During the course of the study, the assays used to measure the anti-D, anti-T, anti-PT, anti-FHA and anti-PRN IgG concentrations were re-developed and re-validated and both assay units and assay cut-offs were adapted. The new ELISA's for PT, FHA and PRN were calibrated against the WHO International Standard (NIBSC 06/140). This allowed the expression of concentrations measured with the new ELISA's in international units per milliliter (IU/mL) instead of the formerly used ELISA units per milliliter (ELU/mL). The newly validated DTPa ELISA's used in the study have a lower assay cut-off as compared to the one described in the protocol. The current assay cut-off is 0.057 IU/mL for anti-D, 0.043 IU/mL for anti-T, 2.693 IU/mL for anti-PT, 2.046 IU/mL for anti-FHA and 2.187 IU/mL for anti-PRN. An agreement between the old and new ELISAs was shown with regards to the two thresholds of clinical relevance for the DI/TE response (0.1 IU/mL and 1.0 IU/mL) and therefore the clinical endpoints and anti-D and anti-T are unchanged. In the absence of a correlate of protection for the B. pertussis antigens, the pertussis endpoints were redefined based on the assay cut-off (see section 5.7.5 of protocol).
- In addition, following CBER feedback on the anti-D re-validated assay, a calibration factor of 0.543 was applied in the analysis of anti-D in order to align the ELISA assay to the WHO 10/262 reference samples which are measured as 2 IU/mL by Di neutralization. Assay since 54 WHO 10/262 reference samples measured by GSK re-validated ELISA led to GMC was about two fold (1.841) higher than the expected value (2 IU/mL).

- Note: Due to re-validation of all assays, the cut-offs presented in Table 11 of the protocol of few antigens have changed. Below table has an updated threshold.

Antigen	Threshold for positivity
• Anti-PT	• 2.693 IU/mL
• Anti-FHA	• 2.046 IU/mL
• Anti-PRN	• 2.187 IU/mL
• Anti-D	• 0.057 IU/mL
• Anti-T	• 0.043 IU/mL
• Anti-polio	• 8 dilution
• Anti-PRP	• 0.066 µg/mL
• Anti-HBs	• 6.2 mIU/mL
• Anti-pneumococcal serotypes (1)	• 0.080 µg/mL
• Anti-pneumococcal serotypes (3)	• 0.075 µg/mL
• Anti-pneumococcal serotypes (4)	• 0.061 µg/mL
• Anti-pneumococcal serotypes (5)	• 0.198 µg/mL
• Anti-pneumococcal serotypes (6A)	• 0.111 µg/mL
• Anti-pneumococcal serotypes (6B)	• 0.102 µg/mL
• Anti-pneumococcal serotypes (7F)	• 0.063 µg/mL
• Anti-pneumococcal serotypes (9V)	• 0.066 µg/mL
• Anti-pneumococcal serotypes (14)	• 0.160 µg/mL

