11.2.4. Immunogenicity

For a given subject and given immunogenicity measurement, missing or non-evaluable measurements will not be replaced. Therefore, an analysis will exclude subjects with missing or non-evaluable measurements.

The Geometric Mean Concentrations/Titres (GMC/Ts) calculations are performed by taking the anti-log of the mean of the log titre transformations. Antibody titres below the cut-off of the assay will be given an arbitrary value of half the cut-off of the assay for the purpose of GMT calculation. The cut-off value is defined by the laboratory before the analysis and is described in the protocol.

A seronegative subject is a subject whose antibody titre is below the cut-off value of the assay. A seropositive subject is a subject whose antibody titre is greater than or equal to the cut-off value of the assay.

The assay cut-off is the value under which there is no quantifiable result available. For an assay with a specific 'cut_off', numerical immunogenicity result is derived from a character field (rawres):

If rawres is 'NEG' or '-' or '(-)', numeric result= cutt_off/2,

if rawres is 'POS' or '+' or '(+)', numeric result = cut_off,

if rawres is '< value' and value<=cut_off, numeric result =cut_off/2,

if rawres is '< value' and value>cut_off, numeric result =value,

if rawres is '> value' and value<cut_off, numeric result =cut_off/2,

if rawres is '> value' and value>=cut_off, numeric result =value,

if rawres is '<= value' or '>= value' and value<cut_off, numeric result =cut_off/2,

if rawres is '<= value' or '>= value' and value>=cut_off, numeric result =value,

if rawres is a value < cut_off, numeric result = cut_off/2,

if rawres is a value >= cut_off, numeric result = rawres,

if rawres is a value >= cut_off, numeric result = rawres,

else numeric result is left blank.

All CI computed will be two-sided 95% CI.

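### SAP 11.2.4 scores a `<value` assay result above the cut-off at its upper bound, so a serum known only to lie below a level can be counted as having reached it

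*SAP*

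**What the plan says.** SAP 11.2.4 lists how each reported string becomes a numeric result. For upper bounds it has two branches. At or below the cut-off: "if rawres is '< value' and value<=cut_off, numeric result =cut_off/2". Above it: "if rawres is '< value' and value>cut_off, numeric result =value". A further line covers the inclusive forms: "if rawres is '<= value' or '>= value' and value>=cut_off, numeric result =value". For lower bounds under the cut-off: "if rawres is '> value' and value<cut_off, numeric result =cut_off/2". The inclusive `>=value` below the cut-off is also given half the cut-off.

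The endpoints are then read off the numeric result. SAP 11.2.4: "A seropositive subject is a subject whose antibody titre is greater than or equal to the cut-off value of the assay". SAP 4.1: "A seroprotected subject is a subject whose antibody concentration/titre is greater than or equal to the level defining clinical protection". SAP 9 gives the current cut-offs: "0.057 IU/mL for anti-D, 0.043 IU/mL for anti-T, 2.693 IU/mL for anti-PT, 2.046 IU/mL for anti-FHA and 2.187 IU/mL for anti-PRN". Its table adds 0.066 µg/mL for anti-PRP, 6.2 mIU/mL for anti-HBs and 8 for polio.

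SAP 11.2.4 also states that "missing or non-evaluable measurements will not be replaced", and it leaves blank any string that fits none of its lines. It does not flag `<value` results above the cut-off, ask for a retest, count them or plan a sensitivity analysis.

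**The concern.** A `<value` report says that the true concentration is somewhere below the value. Entering the value itself gives the serum the smallest number that the report rules out. Where the bound equals a protective threshold, the rule does more than resolve an unknown favourably: it reverses what the laboratory reported. The mirror line has the opposite fault, because a lower bound under the cut-off cannot establish that a serum is seronegative.

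Both primary endpoint families depend on these numbers: seroprotection for diphtheria, tetanus, HBs, polio and PRP, and vaccine response for PT, FHA and PRN. The secondary seropositivity rates and GMCs/GMTs use them too. What is at stake is wrong classification of individual infants each time one of these lines applies.

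**Working it through.** **1. When does the rule produce seroprotection?** For an upper bound v above the cut-off c, the rule gives the numeric result v. It is seropositive because v > c, and seroprotected if v ≥ t, that is, if v/c ≥ t/c. Cut-offs are from SAP 9 and thresholds from SAP 4.1.

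| Antigen | c | t | t/c | Example report | Scored as | What the report proves |
|---|---|---|---|---|---|---|
| Diphtheria | 0.057 | 0.1 | 1.75 | `<0.1` | 0.1, seroprotected | not seroprotected |
| Tetanus | 0.043 | 0.1 | 2.33 | `<0.1` | 0.1, seroprotected | not seroprotected |
| PRP | 0.066 | 0.15 | 2.27 | `<0.15` | 0.15, seroprotected | not seroprotected |
| HBs | 6.2 | 10 | 1.61 | `<10` | 10, seroprotected | not seroprotected |
| Polio | 8 | 8 | 1.00 | `<16` | 16, seroprotected | undetermined |

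Below the threshold only seropositivity is affected: diphtheria `<0.086` is scored seropositive but not seroprotected. For pertussis, PT `<5.386` is scored 5.386 and seropositive, although the true value may be under 2.693.

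**2. Pertussis vaccine response.** Let the pre-dose result be `<b` with b > c, and the post-dose value y.
- If y ≥ b, the infant is a responder whatever the true baseline. The rule agrees.
- If y < c, the infant is a non-responder whatever the true baseline. The rule agrees.
- If c ≤ y < b, response is undetermined. The rule says non-response. Example: pre `<4c`, post 3c.

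If instead the post-dose result is `<b` with b > c, and the infant was seronegative before, the rule always declares a response although the true value may be under c. The error can go either way, and on the pre-dose side only in the middle band.

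**3. Size for a rate (assumed counts).** The plan states no figure for this rule. As a check on the interval method, the exact 95% CI for 226/238 is 91.4 to 97.4, which matches the 95% row for 238 subjects in protocol Table 22. Suppose k of the 226 are `<value` results scored as seroprotected.

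| k (share of 238) | As scored | All k truly negative | All k excluded |
|---|---|---|---|
| 2 (0.8%) | 95.0% | 224/238 = 94.1% (90.3–96.7) | 224/236 = 94.9% (91.3–97.3) |
| 5 (2.1%) | 95.0% | 221/238 = 92.9% (88.8–95.8) | 221/233 = 94.8% (91.2–97.3) |
| 12 (5.0%) | 95.0% | 214/238 = 89.9% (85.4–93.4) | 214/226 = 94.7% (90.9–97.2) |

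The third column is a worst case for bounds above the threshold. For bounds equal to it, such as `<0.1` for tetanus, it is simply the correct count. The last column shows that exclusion alone barely moves the estimate even when every affected serum is negative.

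**4. Size for a GMC (assumed shares).** If a share f of sera would be scored c/2 as negatives but is scored m × c, the GMC is multiplied by (mc ÷ c/2)^f = (2m)^f. For m from 2 to 10, f = 1% gives 1.014 to 1.030 and f = 5% gives 1.072 to 1.162. This too assumes that every such serum is below the cut-off.

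**The case against.** The strongest reply is that the branch may never be used. The SAP defines the cut-off as the level under which no quantifiable result exists, so an ordinary low result should arrive as `<value` at or below the cut-off and be scored at half of it. The disputed line belongs to a standard derivation list, the documents give no count of results it would catch, and every analysis is descriptive, with no test or success criterion. All of this stands. It limits how much the point matters, but the line remains wrong whenever it applies.

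Four stronger readings are tempting and are not supported:
- **That rates and GMCs are inflated overall.** The mirror line, and the line that enters `>value` above the cut-off at its lower bound, push downwards. An overstated baseline can lower the vaccine response rate.
- **That Control infants are hit harder**, because small pre-dose samples would be diluted and reported as `<value`. Nothing says that samples are diluted or that reporting limits rise with dilution. Protocol 5.7.4.1 handles short volume by priority rank, with the pertussis antigens first.
- **That the line contradicts the no-replacement rule.** A `<value` string is a reported result, and the SAP does not define non-evaluable. The most that can be said is that the two sit uneasily together.
- **That `<0.1` and `<0.15` reports must be present**, because these were the protocol Table 11 cut-offs. SAP 9 describes re-validated assays with lower cut-offs, and nothing shows that any result was reported against the old ones.

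Setting every such result to blank would also be a poor remedy. It discards results whose bound already settles the endpoint and, as the last column of the rate table shows, leaves nearly all of any bias in place.

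**Conclusion.** The point holds as a fault in a stated derivation rule. Whenever a `<value` or `<=value` result above the cut-off occurs, it is classed seropositive without proof. It is also classed seroprotected if the bound reaches the threshold, which is automatic for polio and conditional for diphtheria, tetanus, PRP and HBs. When a `<value` bound equals the threshold, a proven negative becomes a positive. When `>value` lies below the cut-off, the serum is called seronegative without proof.

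The practical size is unknown. At assumed shares of about 1% to 5%, a 95% rate could be overstated by about 1 to 5 points if every affected serum were negative. If there are no such results, the effect is nil. The rule deserves correction because it reaches the primary endpoints and is cheap to change. It does not support a claim of net upward bias or of bias between groups.

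**What to change.** Amend SAP 11.2.4 so that each endpoint is classified from what the bound proves, with the threshold being the protective level for seroprotection and the assay cut-off for seropositivity:

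1. `<value` with value at or below the threshold is negative for that endpoint. `<=value` is negative if value is strictly below it.
2. `>value` or `>=value` with value at or above the threshold is positive.
3. Where the bound straddles the threshold, or leaves the pre/post comparison for pertussis vaccine response open, the result is indeterminate for that endpoint. Retest only if serum remains.
4. Add a sensitivity analysis that counts indeterminate `<value` results as negative for the endpoint concerned.
5. Do not enter an upper bound as an observed value in a GMC or GMT unless a sensitivity analysis goes with it.
6. Footnote the number of such results by antigen, group and timepoint. If it is zero throughout, that statement closes the matter.

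The cost is a few lines of SAP wording, a little programming, and possibly a few results that become indeterminate. No new data collection is needed beyond any retest.

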11.2.5. Safety

For analysis of solicited, unsolicited adverse events such as serious adverse events or adverse events by primary MedDRA term, and for the analysis of concomitant medications, all vaccinated subjects will be considered. Subjects who did not report the event or the concomitant medication will be considered as subjects without the event or the concomitant medication respectively.

For a given subject and the analysis of solicited adverse events within 4 days post-vaccination, missing or non-evaluable measurements will not be replaced. Therefore, the analysis of the solicited adverse events based on the Total Vaccinated Cohort will include only vaccinated subjects for doses with documented safety data (i.e., symptom screen completed). More specifically the following rules will be used:

- Subjects who documented the absence of a solicited adverse events after one dose will be considered not having that adverse events after that dose.
- Subjects who documented the presence of a solicited symptom and fully or partially recorded daily measurement over the solicited period will be included in the summaries at that dose and classified according to their maximum observed daily recording over the solicited period.
- Subjects who documented the presence of a solicited symptom after one dose without having recorded any daily measurement will be assigned to the lowest intensity category at that dose (i.e., 37.5°C for fever or grade 1 for other symptoms).
- Doses without symptom sheets documented will be excluded.
- The intensity of the following solicited adverse events will be assessed as described in the below table

Table 4 Intensity scales for solicited symptoms in infants less than 6 years of age

Adverse Event	Intensity grade	Parameter
Pain at injection site	0	None
	1	Mild: Minor reaction to touch
	2	Moderate: Cries/protests on touch
	3	Severe: Cries when limb is moved/spontaneously painful
Redness at injection site		Record greatest surface diameter in mm
Swelling at injection site		Record greatest surface diameter in mm
Fever*		Record temperature in °C/°F
Irritability/Fussiness	0	Behaviour as usual
	1	Mild: Crying more than usual/no effect on normal activity
	2	Moderate: Crying more than usual/interferes with normal activity
	3	Severe: Crying that cannot be comforted/prevents normal activity
Drowsiness	0	Behaviour as usual
	1	Mild: Drowsiness easily tolerated
	2	Moderate: Drowsiness that interferes with normal activity
	3	Severe: Drowsiness that prevents normal activity
Loss of appetite	0	Appetite as usual
	1	Mild: Eating less than usual/no effect on normal activity
	2	Moderate: Eating less than usual/interferes with normal activity
	3	Severe: Not eating at all

*Fever is defined as temperature $\geq 37.5^{\circ}\text{C}$ / 99.5°F for oral, axillary or tympanic route, or $\geq 38.0^{\circ}\text{C}$ / 100.4°F for rectal route. The preferred route for recording temperature in this study will be rectal/axillary.

The maximum intensity of local injection site redness/swelling will be scored at GSK Biologicals as follows:

0	Absent
1	≤ 5 mm
2	> 5 mm and ≤ 20 mm
3	> 20 mm

The maximum intensity of fever (oral, axillary or tympanic route) will be scored at GSK Biologicals as follows:

Grade	Temperature
0	$<37.5^{\circ}\text{C}$
1	$\geq 37.5^{\circ}\text{C}$ to $\leq 38.0^{\circ}\text{C}$
2	$>38.0^{\circ}\text{C}$ to $\leq 39.0^{\circ}\text{C}$
3	$> 39.0^{\circ}\text{C}$

The investigator will assess the maximum intensity that occurred over the duration of the event for all unsolicited AEs (including SAEs) recorded during the study. The assessment will be based on the investigator's clinical judgement.

The intensity should be assigned to one of the following categories:

- 1 (mild) = An AE which is easily tolerated by the subject, causing minimal discomfort and not interfering with everyday activities.
- 2 (moderate) = An AE which is sufficiently discomforting to interfere with normal everyday activities.
- 3 (severe) = An AE which prevents normal, everyday activities (in a young child, such an AE would, for example, prevent attendance at school/kindergarten/a day-care centre and would cause the parent(s)/LAR(s) to seek medical advice.

An AE that is assessed as Grade 3 (severe) should not be confused with a SAE. Grade 3 is a category used for rating the intensity of an event; and both AEs and SAEs can be assessed as Grade 3. An event is defined as 'serious' when it meets one of the pre-defined outcomes as described in Section 8.1.2 in the protocol.

The way the percentage of subjects will be derived will depend on the event analysed (see table below for details). As a result, the N value will differ from one table to another.

Event	N used for deriving % per subject	N used for deriving % per dose
Concomitant vaccination	All subjects with study vaccine administered	All study visits with study vaccine administered
Solicited general AEs	All subjects with at least one solicited general AE documented as either present or absent (i.e., symptom screen completed)	All study visits with study vaccine administered and with at least one solicited general AE documented as either present or absent (i.e., symptom screen completed)
Solicited local AEs	All subjects with at least one solicited local AE documented as either present or absent (i.e., symptom screen completed)	All study visits with study vaccine administered and with at least one solicited local AE documented as either present or absent (i.e., AE screen completed)
Unsolicited AEs	All subjects with study vaccine administered	All study visits with study vaccine administered
Concomitant medication	All subjects with study vaccine administered	All study visits with study vaccine administered

11.2.6. Number of decimals displayed:

The following decimal description from the decision rules will be used for the demography, immunogenicity and safety/reactogenicity.

Display Table	Parameters	Number of decimal digits
Demographic characteristics	Mean, median age	1
Demographic characteristics	SD (age)	1
Immunogenicity	GMT/GMC	3 for anti-D, anti-T and anti-PRP 2 for Strepto antigens 1 for anti-PT, anti-FHA and anti-PRN, anti-HBs, anti-Polio 1, anti-Polio 2 and anti-Polio 3
Reactogenicity	Mean, Min, Q1, Median, Q3, Max for duration	1
All summaries	% of count, including LL & UL of CI	1

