8.2.3.2. Assessment of adverse events**8.2.3.2.1. Assessment of intensity**

The intensity of the following solicited AEs will be assessed as described:

Table 20 Intensity scales for solicited symptoms in infants less than 6 years of age

Adverse Event	Intensity grade	Parameter
Pain at injection site	0	None
	1	Mild: Minor reaction to touch
	2	Moderate: Cries/protests on touch
	3	Severe: Cries when limb is moved/spontaneously painful
Redness at injection site		Record greatest surface diameter in mm
Swelling at injection site		Record greatest surface diameter in mm
Fever*		Record temperature in °C/°F
Irritability/Fussiness	0	Behaviour as usual
	1	Mild: Crying more than usual/no effect on normal activity
	2	Moderate: Crying more than usual/interferes with normal activity
	3	Severe: Crying that cannot be comforted/prevents normal activity
Drowsiness	0	Behaviour as usual
	1	Mild: Drowsiness easily tolerated
	2	Moderate: Drowsiness that interferes with normal activity
	3	Severe: Drowsiness that prevents normal activity
Loss of appetite	0	Appetite as usual
	1	Mild: Eating less than usual/no effect on normal activity
	2	Moderate: Eating less than usual/interferes with normal activity
	3	Severe: Not eating at all

*Fever is defined as temperature $\geq 37.5^{\circ}\text{C} / 99.5^{\circ}\text{F}$ for oral, axillary or tympanic route, or $\geq 38.0^{\circ}\text{C} / 100.4^{\circ}\text{F}$ for rectal route. The preferred route for recording temperature in this study will be rectal/axillary.

The maximum intensity of local injection site redness/swelling will be scored at GSK Biologicals as follows:

- 0 : Absent
- 1 : ≤ 5 mm
- 2 : > 5 mm and ≤ 20 mm
- 3 : > 20 mm

The maximum intensity of fever (*oral, axillary or tympanic route*) will be scored at GSK Biologicals as follows: (*Amended 06 September 2016*)

- 0 = $< 37.5^{\circ}\text{C}$
- 1 = $\geq 37.5^{\circ}\text{C}$ to $\leq 38.0^{\circ}\text{C}$
- 2 = $> 38.0^{\circ}\text{C}$ to $\leq 39.0^{\circ}\text{C}$
- 3 = $> 39.0^{\circ}\text{C}$

All solicited local (injection site) reactions will be considered causally related to vaccination. Causality of all other AEs should be assessed by the investigator using the following question:

Is there a reasonable possibility that the AE may have been caused by the investigational vaccine?

- YES : There is a reasonable possibility that the vaccines contributed to the AE.

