6.4. Analysis of safety

6.4.1. Analysis of safety and reactogenicity planned in the protocol

The primary analysis will be based on the TVC. If more than 5% of enrolled subjects are excluded from the ATP cohort for analysis of safety, then a second analysis based on this ATP cohort will be performed to complement the TVC analysis. All analyses will be descriptive.

- The percentage of doses and of subjects with at least one local symptom (solicited or unsolicited), with at least one general symptom (solicited or unsolicited) and with any symptom (solicited or unsolicited) during the 4-day (Day 0-Day 3) solicited follow-up period will be tabulated with exact 95% CI [Clopper, 1934] after each vaccine dose and overall. The same calculations will be done for symptoms (solicited or unsolicited) rated as grade 3 in intensity, for symptoms (solicited or unsolicited) leading to medical advice and for symptoms (solicited or unsolicited) assessed as causally related to vaccination.

- The percentage of doses and of subjects reporting each individual solicited local and general symptom during the 4-day (Day 0-Day 3) solicited follow-up period will be tabulated after each vaccine dose and overall, with exact 95% CI [Clopper, 1934]. The same calculations will be done for each individual solicited symptom rated as grade 3 in intensity and for each individual solicited symptom assessed as causally related to vaccination.
- All computations mentioned above will be done for grade ≥ 2 (solicited symptoms only) and grade 3 symptoms, for symptoms considered related to vaccination (general symptoms only) and for symptoms that resulted in a medically-attended visit.
- Occurrence of fever and related fever will be reported per 0.5°C cumulative temperature increments as well as the occurrence of grade 3 fever ($> 39.0^\circ\text{C}$ axillary temperature) with causal relationship to vaccination.

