11.2.3. Demography

Age: Age at the reference activity, computed as the number of units between the date of birth and the reference activity.

Conversion of weight to kg

The following conversion rule is used:

Weight in Kilogram= weight in Pounds / 2.2

Weight in Kilogram =weight in oncs / 35.2

The result is rounded to 2 decimals.

Conversion of height to cm

The following conversion rule is used:

Height in Centimetres = Height in Feet * 30.48

Height in Centimetres = Height in Inch * 2.54

The result is rounded to the unit (i.e no decimal)

Conversion of temperature to °C

The following conversion rule is used:

Temperature in °Celsius = ((Temperature in °Fahrenheit -32) *5)/9

The result is rounded to 1 decimal.

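### Does the lack of a rectal fever grade scale in the SAP leave the grade ≥2 and grade 3 fever percentages undefined?

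*SAP*

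**What the plan says.** The footnote to SAP Table 4 (section 11.2.5) sets fever at 37.5°C or above by mouth, armpit or ear, and at 38.0°C or above rectally. It adds: "The preferred route for recording temperature in this study will be rectal/axillary". The grade scale follows, with the lead-in "The maximum intensity of fever (oral, axillary or tympanic route) will be scored at GSK Biologicals as follows": grade 0 below 37.5°C, grade 1 from 37.5 to 38.0°C, grade 2 above 38.0 and up to 39.0°C, grade 3 above 39.0°C. The section then moves on to the intensity of unsolicited events. The only temperature conversion, in SAP 11.2.3, is "Temperature in °Celsius = ((Temperature in °Fahrenheit -32) *5)/9", which changes units and not routes.

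SAP 6.4.1 plans percentages for solicited symptoms of grade 2 or higher and of grade 3, and a combined summary: "The same calculations will be done for symptoms (solicited or unsolicited) rated as grade 3 in intensity". It also plans fever in cumulative 0.5°C steps, and describes grade 3 fever by the cut-off above 39.0°C, "axillary temperature) with causal relationship to vaccination". Template 19 labels its temperature rows as axillary.

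SAP 11.2.5 also has a rule on inclusion. A subject with a solicited symptom reported as present and at least some daily values recorded enters the summary for that dose and is graded on the highest value. The denominator for general symptoms is "All subjects with at least one solicited general AE documented as either present or absent".

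**The concern.** One of the two preferred routes has no grade scale. Read literally, a rectal fever is either ungraded or graded on cut-offs written for routes with a lower fever limit.

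If rectal fevers were left ungraded while their infants stayed in the denominator, the grade ≥2 and grade 3 percentages would be too low by the share of such fevers measured rectally. If the printed cut-offs were used, the same grade would sit closer to the fever limit for rectal readings than for the others. Either way, a planned safety output would depend on a rule that is not written down. Fever is also a named risk: Protocol 1.3.1 and 6.6 note higher fever rates when the two study vaccines are given together.

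**Working it through.** The plan gives no figure to reproduce, so the check has two parts: whether the rules already in the SAP exclude rectal fevers, and how much the grading choice can move.

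**Inputs.** The scale, the two fever limits, the inclusion rule and the denominator are from SAP 11.2.5. Readings are taken to one decimal, the rounding in SAP 11.2.3. The 0.5°C steps are from SAP 6.4.1 and the row cut-offs from Template 19.

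**1. Are rectal fevers left out?** If they were, reported percentage = (1 − r) × percentage with all routes graded, where r is the rectal share of such fevers. A recorded rectal temperature is not a missing value, however, and the inclusion rule requires it to be counted and classified. The factor (1 − r) therefore does not follow from the plan.

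**2. Distance above the fever limit on the printed scale.** At one decimal, grade 2 starts at 38.1°C and grade 3 at 39.1°C.

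| | Rectal | Other routes |
|---|---|---|
| Grade 2 starts above limit by | 38.1 − 38.0 = 0.1°C | 38.1 − 37.5 = 0.6°C |
| Grade 3 starts above limit by | 39.1 − 38.0 = 1.1°C | 39.1 − 37.5 = 1.6°C |

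This is a difference in labelling. The documents do not say that grades should be equally far from the limit for each route.

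**3. Where does the choice change a grade?** Let g(t) be the printed scale. Compare g(t) with g(t − 0.5) for rectal readings t from 37.0 to 40.0°C. The shift is 38.0 − 37.5 = 0.5°C; it is an assumption used to show the range, not a proposed rule.

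| Rectal reading | g(t) | g(t − 0.5) |
|---|---|---|
| 37.5–37.9°C | 1 | 0 |
| 38.1–38.5°C | 2 | 1 |
| 39.1–39.5°C | 3 | 2 |
| all others | same | same |

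The first band is settled by the Table 4 footnote: a rectal reading below 38.0°C is not fever, so there is no fever to grade. The choice matters only in the other two bands.

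**4. What would the reader still see?** Template 19 has rows above 38.0, 38.5, 39.0 and 39.5°C.

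- Printed scale: grade ≥2 means above 38.0°C and grade 3 means above 39.0°C.
- Shifted scale, rectal readings: t − 0.5 > 38.0 gives t > 38.5, and t − 0.5 > 39.0 gives t > 39.5.
- Other routes keep the printed cut-offs.

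For any route mix, the grade ≥2 percentage under the shifted scale therefore lies between the >38.5 and >38.0 rows, and the grade 3 percentage between the >39.5 and >39.0 rows. This holds if the increment rows pool readings from all routes. The choice is then bounded by adjacent rows of a table that is already planned.

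**5. Fever reported with no value.** SAP 11.2.5 assigns these to the lowest category, labelled 37.5°C. That is below the rectal limit, but it cannot reach the grade ≥2 or grade 3 rows.

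**The case for a change.** The strongest case for a change is that a descriptive percentage still needs a defined numerator. Here the undefined part concerns a preferred route and an expected reaction, and grade 3 general solicited events are among the data the monitoring committee receives (Protocol 5.4.1). Template 19's axillary label can be adapted (SAP section 12), but the missing rule is in the body of the SAP, and SAP section 10 describes the table of contents for outputs as a list, not a set of derivations. The combined grade 3 summary (Template 17) needs a fever grade directly and has no temperature rows beside it.

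The factual core of this stands: the SAP does not state how a rectal reading is graded, and its axillary wording does not fit a study that allows rectal readings. It is also too firm to say that any-fever incidence is beyond doubt. The printed scale alone would call rectal 37.5–37.9°C grade 1, and it takes the footnote to correct that.

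What does not stand is the step to a wrong or unusable result. The inclusion rule closes off omission. The output list, which is not available here, may already separate routes. The protocol cannot be cited as confirmation: its section 8.2.3.2.1 has the same restricted scale, but the available text then runs straight on to causality, so material may be missing there. Only the statement about the SAP is secure.

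**Conclusion.** This is missing detail that an analyst can fill sensibly, and no change to the plan follows. The route-specific fever definition decides whether a rectal reading is fever, the inclusion rule keeps it in the summary, and the remaining choice affects only readings of 38.1–38.5°C and 39.1–39.5°C. A programmer would fix that choice in the derivation specification and describe it in a table footnote.

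The size in percentage points cannot be determined, because neither the route mix nor the fever distribution is given. Three facts limit the consequence. Fever is a secondary safety output, all analyses are descriptive, and the 0.5°C steps show the distribution whatever grade label is used. The contrast between the dTpa and Control groups is little affected if route use is similar in the two. That is an assumption, but a reasonable one, since site staff are to remain blinded to the mothers' allocation (Protocol 5.3).

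Writing by-route tables into the plan would bring little gain. It would split the 601 infants tabulated in SAP 6.3.2 and would need the route of every reading, whose capture the documents imply but do not state. The conclusion would differ only if rectal readings were in fact omitted, which would breach the SAP's own inclusion rule.
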